### **Research Design and Methods**

#### *Design*

This 3-year, mixed methods modified, non-randomized trial will follow individuals for two years. Due to the inability to recruit veterans interested in participating in a control (no dog) group, this group has been eliminated going forward with the study. The study will examine the influence of SDs by assessing the longitudinal change in mental health assessment over time among veterans who have PTSD. The group will consist of individuals partnered with SDs. Following initial screening for inclusion criteria, including criteria set by dog vendors, subjects who are eligible will receive a SD. This study will measure changes over time in the primary outcome of mental health. Additional outcomes in psychosocial health and healthcare utilization will be included. Recruits successfully completing the screening process will be placed on a vendor's waiting list to receive a SD upon the dog's completion of training. Recruits who do not meet all criteria, including vendor criteria, will be ineligible to participate..

Data will be collected at baseline and at 3, 6, 9, 12, 18 and 24 months for individuals with service dogs. For those awaiting service dogs, repeated assessments will occur every 3 months until obtaining a SD. Once baseline data has been collected for 24 months, assessments will occur every 6 months until the Veteran is paired with a SD. Baseline data will include detailed information on the characteristics of the participants, their mental health, psychosocial well-being, socioeconomic and healthcare utilization characteristics. As we want to obtain information regarding the changes in health and wellbeing over time, a prospective study will permit this type of comparison.

*Sample:* The study will use a convenience sample of VHA patients who are currently in treatment for PTSD. We have chosen to use these criteria as a safety measure for the veteran and the dogs. At this time, there are currently 600 veterans receiving care at James A. Haley VAMC for PTSD, with an estimated 25 new veterans seen in the clinic per week. We are confident that an adequate number of Veterans will be recruited for the study. We will monitor recruitment and retention numbers on a monthly basis. The use of additional VA hospitals as a potential source for recruitment is the contingency plan should we be unable to meet enrollment numbers.

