We will be enrolling up to 220 Veterans to be paired with service dogs. The previously cited longitudinal study had only an eight percent attrition rate. Although similar methods are included in this proposal, we recognize that this is a different population; we will plan on a higher attrition rate. Thus, we are estimating a 15 percent drop-out rate ( $n=33$ ), and we will over-recruit participants. Up to two hundred and twenty participants will be recruited over the course of the study. These recruitment numbers are chosen with the expectation that *200 individuals* will complete the study.

A repeated measures design with one fixed effects (any one covariate [TBD]) and 1 within subject effect (time; each subject is measured 5 times [minimum]) achieves approximately 100% power to test the primary fixed effect (dog group status) if a Geisser-Greenhouse Corrected F Test is used with an alpha level=5% and the actual effect  $SD=0.47$  (effect size=5.54). Further, this design achieves approximately 100% power to detect a significant effects among both covariates (alpha level=5%,  $SD=0.8$ ; effect size=5.54) and significant interaction between both the primary fixed effect (dog group status) and each of the covariates (alpha level=5%,  $SD=0.8$ ; effect size=5.54). This analysis assumes a 1st order auto correlation between repeated assessments equal to 0.80.

To assure that we recruit sufficient sample size, we will initiate the following strategies: (1) carefully consider respondent burden when finalizing the baseline survey and interview schedule, (2) employ and train research assistants/data collectors with previous experience in collecting data and who have good communication skills, (3) provide a small reimbursement (\$10.00) for participant time and effort each time a questionnaire is returned, (4) develop posters and recruitment flyers which will be displayed in all mental health clinical areas, and (5) provide in-services on a regular basis to the PTSD and other mental health clinicians explaining the study. These methods have been used successfully in the past by the research team.

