**Analysis:** The distribution of each variable will be examined for outliers to determine if transformations (to normalize data) are necessary. Initially, means  $\pm$  SD, and medians, will be calculated for all continuous measures (e.g., age, psychological scales). Frequencies and percent will be determined for categorical variables (e.g., gender, race, etc.). Variables considered ‘confounders’ (demographic and dog predisposition questionnaires) would be compared across time for the relevant hypotheses. Categorical variables (e.g., gender, race, disability) will be compared across groups using chi-square. Continuous variables (years of disability, dog predisposition scores) will be compared using ANOVA. Baseline differences will be noted and controlled for in additional analyses. A significance level of ( $\alpha < 0.05$ ) will be used for all analyses. All data will be managed as intent to treat.

Statistical Analyses are presented below by hypothesis:

**Hypothesis 1A:** *Individuals partnered with SDs will have greater improved mental health over time.* Baseline data will be examined. Observed significant differences will be used as covariates in modeling, they will be controlled in subsequent analysis. For this hypothesis, a linear repeated measures mixed model will be used to determine changes over time between groups. PCL-checklist scores will be considered the dependent variable. Baseline PCL-C scores will be introduced in all models as covariates. These scores are continuous. The use of mixed models allows for control of covariance data expected in clustered and repeatedly sampled data, and missing data. We expect the SD group to have greater functional independence and community participation at the end of the study.

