**Hypothesis 1B:** *Improvements in secondary factors of physical, psychosocial, and socioeconomic variables will be seen in the SD group over time.* Variables within the physical (medication, comorbidities), psychosocial (affect, depression, loneliness) and socioeconomics (healthcare utilization) will be compared over time and will be assessed for each variable of interest using a repeated measures mixed model for dependent variable (DV) scored a continuous scale and generalized estimating equations (GEE) models for DV variables scored as a categorical. Dependent variables for all models will be scale or subscale scores. The within-participants variable will be the score at each time point (baseline, 3, 9, 12, 18 and 24 months). If significant differences exist at baseline for any confounding variables, that factor will be controlled for in the analysis. We expect to show improvements in all characteristics over the course of the study.

We will also complete a multivariate logistic regression to determine predictors of success (dichotomized higher scores after 18 months on function and participation). We expect that improvements in psychosocial factors (e.g, community participation) will result. We expect the data to be normally distributed; therefore, linear regression will be used. Results from the previous hypotheses (1B) will be used to determine which predictor variables are entered into the regression model; any variable with a  $p$ -value less than 0.10 will be considered. Highly related variables will be entered into the model separately. Any confounders significant at baseline will

Dogs and PTSD: V11: 11.26.14

be controlled for in the models. In addition, we will repeat the multivariate logistic regression analysis described above with group (SD vs. control) as a primary fixed variable. We expect that subjects paired with a SD will demonstrate increased improvement in psychosocial factors.

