Power analysis for Hypotheses 1: All power analyses were completed with PASS 6.0^81. Given a minimum sample size of 65 (per group), and an alpha of 0.05, we have over 80 percent power to detect differences in socioeconomic characteristics. This power analysis is based on changes in mean and SD (PCL-C) from prior published studies. This power analysis allows for the addition of three covariates to be added to the model.

***Hypothesis 2A:*** *Individuals partnered with SDs will have decreased mental health care utilization, over time.* We expect the SD group to experience diminished healthcare utilization over time. A within subject repeated measures will be completed to determine changes over time for healthcare utilization.

***Hypothesis 2B:*** *Individuals partnered with SDs will have decreased overall health care utilization, over time.* We expect the SD group to experience diminished healthcare utilization over time. A within subject repeated measures will be completed to determine changes over time for healthcare utilization.

*Exploratory Aim:* We will compare our findings to data collected in similar study entitled, “A Study of Dog Adoption in Veterans with Posttraumatic Stress Disorder” which is being conducted by [name] at the South Texas Veterans Healthcare System in San Antonio, TX. This is a 2-year pilot study examining the use of shelter dog adoption as a supplement to standard care in reducing PTSD symptoms in Veterans. 24 veterans will be randomized to adopt a dog from the Humane Society while another 24 (control group) will be randomized to a wait-list and be eligible to adopt a dog after 3 months. Outcome measures will be assessed at baseline and at 3 intervals (1, 3, and 6 months post-randomization) for Veterans in the experimental group and 4 intervals (1, 3, 4, and 6 months) for those in the control group. Data collection will be in the form of face-to-face interview as well as self administered paper forms. CPRS records will be reviewed for changes in mental health treatments, medications, diagnoses, and other health related variables. Analysis will be completed which will examine similar measures (e.g. PCL checklist, depression, community integration) across our Veterans who received service dogs at three time points (baseline, three and six months) to their Veterans who received dogs as pets. As this is an exploratory analysis, power analysis was not completed.

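### Apart from baseline PCL, confounders enter the models only after a significant baseline or observed difference, a test with no comparator in a one-group study, and no drop-out comparison is planned

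*Combined protocol and SAP*

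**What the plan says.** The Design section states that the control group could not be recruited and that "this group has been eliminated going forward with the study". What remains is one group: "The group will consist of individuals partnered with SDs".

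The opening Analysis paragraph of Data Management and Statistical Analysis keeps chi-square and ANOVA comparisons across groups. It also says that confounders, described as demographic and dog-predisposition variables, "would be compared across time for the relevant hypotheses". Covariates are then chosen as follows:

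- **Hypothesis 1A:** "Observed significant differences will be used as covariates in modeling, they will be controlled in subsequent analysis".
- **Hypothesis 1B:** "If significant differences exist at baseline for any confounding variables, that factor will be controlled for in the analysis". The regression for predictors of success repeats the baseline condition for confounders, but screens its predictors separately at p below 0.10.
- **Unconditional:** baseline PCL enters all the Hypothesis 1A models, whatever its p-value.

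The number of covariates is not settled. The Sample section plans for one, still to be determined. Under Power analysis for Hypotheses 1, "This power analysis allows for the addition of three covariates to be added to the model".

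On losses, the Sample section says "Up to two hundred and twenty participants will be recruited over the course of the study" and "we are estimating a 15 percent drop-out rate". The Analysis section says that mixed models accommodate missing data and that data are handled by intent to treat. It describes no comparison of Veterans who drop out with those who complete.

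**The concern.** A baseline difference needs two sets of people. With one group there is only one set at baseline, so the condition for adjustment can never be met. The analyst must then either adjust for nothing beyond baseline PCL or choose covariates after seeing the data.

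The only check of confounders that can still be run is the one across time. Gender and race do not change within a Veteran, and age changes only with the calendar. The distribution of such traits can shift between visits only because some Veterans have left. That makes drop-out the issue of interest, and the across-time comparison is a poor way to find it because nearly the same people are counted at each visit.

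At stake is the mean change in PCL. In a one-group before-and-after study, a baseline trait biases that mean if it is linked both to leaving and to the size of the change. Selective loss is plausible here, because the Intervention section withdraws any Veteran who stops PTSD treatment. A lesser point is that disability, years of disability and dog predisposition are named as comparison variables, but neither Table 2 nor the measure descriptions list them.

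**Working it through.** **Inputs from the plan.** Up to 220 enrolled, 15% drop-out, baseline plus six follow-up visits, first-order autocorrelation 0.80, significance level 0.05.

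**Assumed inputs, not in the plan.** PCL SD 12. Drop-outs spread evenly over the six follow-ups. Trait shift in drop-outs of 0.25 to 1.0 SD, or a binary trait with 50% prevalence and a drop-out risk ratio of 1.5 to 3. Trait effects on the 24-month change are given below.

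**Step 1: the plan's drop-out figure.** 0.15 × 220 = 33, which reproduces. It leaves 220 − 33 = 187 completers, not the 200 that the Sample section expects.

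**Step 2: can the across-time comparison see drop-out?** Suppose the 33 differ from the 187 by 0.5 SD on a stable trait.

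- Baseline (all 220) against month 24 (187), treated as independent samples. The mean shifts by (33/220) × 0.5 = 0.075 SD. The standard error is √(1/220 + 1/187) = 0.099, so the expected z is 0.075/0.099 ≈ 0.75.
- The 187 are a subset of the 220, so this z hardly varies. Its true SD is 0.15 × √(1/33 + 1/187) / 0.099 = 0.15 × 0.189/0.099 ≈ 0.28. Reaching 1.96 would take a deviation of (1.96 − 0.75)/0.28, more than 4 SDs.
- Drop-outs against completers directly: z = 0.5/0.189 = 2.65, with power about Φ(2.65 − 1.96) ≈ 75%.

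Simulation with 4,000 runs per setting at 15% loss agrees:

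| Trait in drop-outs | ANOVA or chi-square over 7 visits | Baseline vs month 24 | Drop-outs vs completers |
|---|---|---|---|
| Shift 0.25 SD | 0% | 0% | 26% |
| Shift 0.5 SD | 0% | 0% | 75% |
| Shift 1.0 SD | 0.03% | 7.8% | 99.9% |
| Binary, risk ratio 2 | 0% | 0% | 55% |
| Binary, risk ratio 3 | 0% | 0% | 89% |

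With no selection at all, the across-time test fired in 0% of runs rather than 5%. It is not a valid 5% test here.

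**Step 3: bias in the month-24 change.** Take a binary trait with risk ratio 3 that alters the 24-month change by 10 points. The drop-out risks are 0.225 and 0.075. The trait's share among completers is 0.5 × 0.775/0.85 = 0.456, so the completers-only bias is (0.500 − 0.456) × 10 = 0.44 points. The mixed model without the trait uses the scores seen before drop-out and reduces this to 0.33. Over risk ratios 1.5 to 3 and effects of 5 or 10 points, its bias is 0.07 to 0.33 points.

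For a continuous trait that alters the fall by 3 to 8 points per SD and is raised by about 0.5 to 0.95 SD in drop-outs, the completers-only bias is 0.15 × shift × effect. That runs from 0.15 × 0.5 × 3 = 0.2 to 0.15 × 0.95 × 8 = 1.1 points. The mixed model without the trait gave 0.12 to 0.88. With the trait and its visit interaction the bias was at most 0.04. With the trait as a main effect only, roughly 35 to 80% of the bias remained.

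**Step 4: scale.** The standard error of the mean change is √[2 × 12² × (1 − 0.8⁶)/187] = √(212.5/187) = 1.07 points.

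**The case against.** The strongest reply is that the across-groups wording is left over from the eliminated control group, so this is an editing matter, and that the numbers are small. Four parts of that case stand.

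- A reader might infer that no adjustment at all takes place. The plan does not support that. Baseline PCL is always entered for Hypothesis 1A, and the success and exploratory regressions screen predictors at p below 0.10.
- A reader might infer that an across-time difference triggers adjustment, so that its low detection rate is itself why covariates are left out. The plan states no such link and names no test for that comparison. The near-zero rates apply to one natural way of running it.
- A reader might infer that the fall in PCL will be overstated. That sign was assumed. A trait that raises both drop-out and benefit would bias the result the other way.
- The mixed model recovers part of the bias. In the binary-trait settings it removed about a quarter of the completers-only figure.

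The reply does not rescue the rule. Removing the leftover wording would still leave no stated basis for choosing covariates and no examination of who leaves. The near-zero detection rate is also specific to the planned loss. At 40% drop-out and a risk ratio of 3, the seven-visit comparison fired in 66% of runs for the binary trait. For a continuous trait with a 1.0 SD shift, it fired in 84% at the same loss.

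**Conclusion.** The point holds as a defect in the covariate rule. In a one-group study the significance condition cannot be evaluated, so beyond baseline PCL it selects nothing. The across-time comparison leads to no stated action and is nearly blind to selective loss at 15% drop-out. No comparison of drop-outs with completers is planned.

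The likely numerical effect is modest: roughly 0.1 to 0.9 PCL points at month 24, below one standard error of about 1.07. This rests on the assumed SD, trait effect and strength of selection. The upper end needs a trait effect of 8 points per SD. Greater attrition would enlarge the bias: for the binary trait it was 0.12 to 0.62 points at 25% loss and 0.25 to 1.18 at 40%. The documents do not show that any particular trait drives drop-out, so these figures show what could happen and are not a forecast. The change is worth making because the rule cannot be carried out as written and the remedy is cheap, but the primary result is not shown to be invalid.

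**What to change.** 1. Delete the significance-triggered rule under Hypotheses 1A and 1B, including its repetition in the success model. Keep baseline PCL as an unconditional covariate.
2. Pre-specify a short list from variables already collected, for example age, gender and baseline PHQ-9. Enter each with its visit interaction whatever its p-value. In the depression model, PHQ-9 serves only as that outcome's own baseline. State one covariate count in both the Sample section and the power section.
3. Report the change averaged over the covariate distribution of all paired Veterans.
4. Replace the across-time comparison with a table of standardised baseline differences between Veterans who dropped out and those who completed their scheduled follow-up. The Projected Time Table allows a minimum of 18 months, with 24 for early enrollees, so those who reached only a planned 18 months count as completers.

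**Cost.** SAP wording and no new data. With visit as a category, three covariates add up to 3 × 6 = 18 parameters over the six follow-ups. The adjustment removes only the drop-out bias that the listed covariates explain. Loss driven by events after baseline, such as leaving PTSD treatment, may remain.

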TASK	YEAR 1				YEAR 2				YEAR 3				YEAR 4				YEAR 5			
	Apr 2011	June 2011	Aug 2011	Oct 2011	Jan 2012	Apr 2012	Aug 2012	Oct 2012	Jan 2013	Apr 2013	Aug 2013	Oct 2013	Jan 2014	Apr 2014	Aug 2014	Oct 2014	Jan 2015	Apr 2015	Aug 2015	Oct 2015
Start up activities, finalize data collection forms, hire and train data collectors	Shaded																			
Renewal training for data collection				Shaded			Shaded													
Advertisement/promotion of study	Shaded	Shaded	Shaded	Shaded																
Recruit participants, collect baseline	Shaded	Shaded	Shaded	Shaded	Shaded															
STUDY HOLD**					Blue	Blue	Blue	Blue	Blue	Blue										
Collect 3-, 6-,9-, 12- 18- and 24-month data on enrolled veterans			Shaded	Shaded	Shaded	Shaded	Shaded	Shaded	Shaded	Shaded	Shaded	Shaded	Shaded	Shaded	Shaded	Shaded	Shaded	Shaded	Shaded	Shaded
Enter data in electronic database and conduct on-going verification			Shaded	Shaded	Shaded	Shaded	Shaded	Shaded	Shaded	Shaded	Shaded	Shaded	Shaded	Shaded	Shaded	Shaded	Shaded	Shaded	Shaded	Shaded
Conduct statistical analyses and summarize findings																				
Apply for additional funding to support follow up work																				
Dissemination of Findings																				
Prepare manuscripts																				Shaded

\*\* Because of ongoing vendor issues, enrollment was stopped for a second time and new vendors have been awarded contracts. Study will extend beyond the three year period utilizing Veterans who signed consent prior to second hold.

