*Screening Visit:* Once a Veteran has agreed to participate in the study, they will be asked to participate in a screening visit. Once the informed consent process is finalized, eligibility criteria will be confirmed. A review of CPRS records will be conducted by the study team to verify the Veteran truly meets all criteria. At this time, if all criteria are met, all baseline questionnaires will be completed and field notes taken. For safety reasons, Veterans who have children younger than 10 years of age in the home for more than 8 hours per day, one day per week or more will be excluded from the study. After 20 dogs have been placed without incident, this criterion will be revisited to potentially allow these Veterans to participate.

- The study team will perform a home evaluation visit prior to referring Veterans to a vendor. This visit will be to ensure the environment is safe and suitable for a

dog. A home environment checklist has been developed and will guide the study team in assessing the environment. An information sheet that provides details to Veterans regarding why and how the home visit will be conducted will be provided to Veterans when Informed Consent is obtained. During the visit, the team will check to see that there is an area for a dog to exercise, relieve itself, sleep, as well as making sure hazardous plants or chemicals are not within reach of a dog. All family members that will be living in the home will be expected to meet with the study team to ensure they understand the study requirements and are on board with bringing a dog into the home. If any issues are identified by the study team during the home evaluation the Veteran will have 3 weeks to fix the issues and reschedule a follow up home evaluation visit. If during the follow up home evaluation the study team determines that the issues are not fully resolved the Veteran will have one additional week to remedy the issues and reschedule a final home evaluation. If the issues remain unresolved the Veteran will be withdrawn from the study. Once the home evaluation has been approved the Veteran will be provided with contact information for the vendor. The Veteran will be instructed to contact the vendor and will be placed on the waiting list. The Veteran will be encouraged to review home owner/rental insurance policy to include a dog and be required to obtain a license for their service dog per local laws.

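### The primary PCL analysis (H1A) and its stated power are still written for a two-group comparison, although the design now has one service-dog group; H1A names no within-person contrast and no single baseline score

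*Combined protocol and SAP*

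**What the plan says.** **Design.** Research Design and Methods, Design, says of the "control (no dog) group, this group has been eliminated going forward with the study". It continues: "The group will consist of individuals partnered with SDs", and "This study will measure changes over time in the primary outcome of mental health". The Sample paragraphs plan up to 220 Veterans, all to be paired with dogs. The timeline footnote adds: "Study will extend beyond the three year period utilizing Veterans who signed consent prior to second hold".

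**Primary analysis.** Under Hypothesis 1A, with PCL as dependent variable, "a linear repeated measures mixed model will be used to determine changes over time between groups". The same paragraph states: "Baseline PCL-C scores will be introduced in all models as covariates". It names no visit and no contrast. Hypotheses 2A and 2B, by comparison, state a within-subject analysis outright.

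**Power.** The Sample section gives about 100% power for dog group status as the primary fixed effect, at 5% alpha with first-order autocorrelation 0.80. Its opening words look partly revised: they list one covariate still to be determined, and time as a within-subject effect. No power is given for time. Power analysis for Hypotheses 1 gives over 80% with 65 per group. It names socioeconomic characteristics as the target while citing PCL-C as the basis.

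**Baseline.** At the Screening Visit, "if all criteria are met, all baseline questionnaires will be completed and field notes taken". The Design section, the waiting-period text and Human Subjects instead treat baseline as a series: at consent, every 3 months, then every 6 months after month 24, with withdrawal if unpaired at 48 months.

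**The concern.** This is the only analysis text for the primary hypothesis, and its contrast does not belong to the design that remains. A replacement would have to be chosen during analysis, possibly with data in hand, and two choices are open: which contrast over time, and which PCL score counts as baseline. Either can change the result. The power figures that should reassure a reader describe a comparison that the study no longer makes.

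**Working it through.** **1. The plan's own power.** Two-group between-subject F test, T = 5 visits, autocorrelation 0.80. The variance factor of a subject's mean is (5 + 2(4×0.8 + 3×0.64 + 2×0.512 + 0.4096))/25 = 18.107/25 = 0.724. The Sample section gives no n per group, so I use the 65 from the later power paragraph. Reading 0.47 as the SD of group means in SD units, the noncentrality is 2×65×0.47²/0.724 = 39.7 and power is 1.000. Using 5.54 instead also gives 1.000. So the figure of about 100% reproduces, but only as a two-group figure. (If 0.47 were a standardized mean difference, power would be 0.88.)

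For 65 per group at a single time point, 80% power corresponds to a standardized difference of 2.80×√(2/65) = 0.491. No difference or SD is printed, so the claim of over 80% can be neither confirmed nor refuted.

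**2. The same model with one group.** Intercept, time, group and group-by-time over six visits make 12 columns. With every subject in the dog group the rank is 6. The group term and all group-by-time terms duplicate the intercept and time terms.

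**3. What is left if only the reference to groups is deleted.** Inputs: N = 220 − 33 = 187 and correlation 0.80 (Sample section); visits at 0, 3, 6, 9, 12, 18 and 24 months. Assumed, not in the documents: PCL SD 12. The correlation is read three ways: decaying per 3 months, decaying per visit, or exchangeable. The time test is a multivariate F with noncentrality N·d′(CΣC′)⁻¹d, where d holds the differences between visits. With baseline a covariate only, d compares follow-up visits with one another. If the benefit is complete by month 3 and held, d = 0, so power equals alpha whatever the SD, N or correlation.

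| Benefit pattern | Covariate only, common slope | Covariate only, visit-specific slopes | Baseline as a response |
|---|---|---|---|
| 3 or 5 points by month 3, held | 5% | 5% | 99-100% |
| Half of 5 points by month 3, rest by month 18 or 24, serial correlation | 36-53% | 48-63% | 99-100% |
| Same, exchangeable | 99-100% | 99-100% | 100% |
| Linear to 5 points by month 18 or 24 | 87-100% | 96-100% | 93-100% |

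**4. Detectable change at month 18.** This is 2.80 × SD × √(2(1 − r)/N), where r, the correlation between baseline and month 18, is 0.8⁶ = 0.262, 0.8⁵ = 0.328 or 0.80.
- N = 187: standard errors 1.07, 1.02 and 0.555; detectable 2.99, 2.85 and 1.55 points.
- N = 65: standard errors 1.81, 1.73 and 0.94; detectable 5.07, 4.84 and 2.64 points.

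The Sample section also expects 200 completers; N = 200 gives 1.5-2.9 points.

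**5. Choice of baseline.** Suppose no dog effect, an assumed background improvement of 1 point per year, and assumed evenly spread waits of 3-12, 3-24 or 3-48 months (means 7.5, 13.5 and 25.5). Apparent change at month 18 from the consent score is (7.5 + 18)/12 = 2.1, (13.5 + 18)/12 = 2.6 or (25.5 + 18)/12 = 3.6 points. From the last score before pairing (mean gap 1.5, 1.5 or 2.3 months) it is 1.6, 1.6 or 1.7. The choice of baseline alone moves the estimate by 0.5 to about 1.9 points, and neither choice removes the drift.

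**The case against.** The intent is plain: the aims and the Design section speak of change over time in Veterans with dogs, so the reference to groups could pass as leftover wording. That much stands, but intent supplies neither a contrast nor a baseline.

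The 5% figure needs three things that the plan does not state: baseline kept out of the response, reliance on an omnibus time test, and a benefit complete by month 3. The text under Hypothesis 1B lists baseline among the time points of the dependent variable, and whether that reaches H1A is unclear. The Projected Time Table expects acclimation to take longer than 18 months, which fits a gradual effect, and there little is lost; visit-specific slopes can even do slightly better than baseline as a response. So a reader might infer that the planned analysis would miss a real benefit. The documents do not support that; they show only that the plan leaves this possible.

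A reader might also infer that no control was ever enrolled. The words about going forward leave that open: no section gives a number of earlier controls or a rule for using them. Nor can the 65-per-group statement be read simply as power for PCL, since its named target is socioeconomic characteristics.

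**Conclusion.** The concern holds. The mismatch between the surviving single-group design and the H1A test is on the page and needs no assumption, and the figure of about 100% power does not apply to anything one group can estimate. It concerns the primary analysis of the primary outcome, so it must be corrected before analysis.

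The sizes in steps 3 and 4 rest on the assumed SD of 12 and on how the 0.80 correlation is read; step 5 rests on assumed drift and waits. Two stronger readings should be resisted. The study is not shown to be underpowered: about 1.55-3.0 points is detectable at month 18 with 187 completers. Nor do the documents make the last pre-pairing PCL the only valid baseline. They show that one must be fixed, and that particular choice depends on PCL being collected during the wait.

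**What to change.** 1. Restate H1A as a within-person mixed model with no group term, with the pre-pairing PCL as a response or an equivalent test of change from it.
2. Fix in advance one baseline score and one primary contrast in months since pairing. The last PCL before pairing is a sensible default if PCL is collected during the wait. The general footnote to the measures tables implies that it is, but the waiting-period text names only feelings, mood and quality of life, so the plan should confirm it. Report change from the consent score as a sensitivity analysis.
3. Replace or withdraw both power statements, giving the detectable change for the chosen contrast with its SD and correlation and their sources.
4. State whether any earlier controls exist and whether they enter H1A. If not, remove the dog-versus-control wording under Hypothesis 1B and in the exploratory analyses.
5. State that this contrast does not separate the dog from change under the ongoing PTSD treatment that the plan requires.

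The cost is rewritten text and a new power basis, with no added visits or data. The downside is candour: the conclusion becomes an uncontrolled within-person change, and the near-100% power claim goes.
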